2.7.2 Statistical hypothesis, model, and method of analysis

Similar to the analysis of primary endpoint, there is no formal hypothesis testing. PFS, OS and DOR will be summarized descriptively using Kaplan-Meier medians and quartiles.

Since there is a single primary endpoint (ORR), supported by secondary endpoints, the nominal level of significance for the primary analysis will not be affected by multiplicity.

PFS based on local investigators review of tumor assessments and using RECIST 1.1 criteria is a secondary endpoint in this trial and will be analyzed using the same conventions as that of the primary efficacy analysis. The distribution of PFS will be estimated using the Kaplan-Meier method. The median PFS along with 95% confidence intervals will be presented.

The survival distribution of OS distribution will be estimated using the Kaplan-Meier method, and Kaplan-Meier curves, medians and 95% confidence intervals [Brookmeyer and Crowley 1982] of the medians intervals.

DOR will be listed and summarized for all subjects in the FAS with confirmed CR or PR. The distribution of duration of response will be estimated using the Kaplan-Meier method and the median duration of response will be presented along with 95% confidence interval only if a sufficient number of responses is observed.

2.7.3 Handling of missing values/censoring/discontinuations

For subjects who have not progressed or died at the time of the PFS or DOR analysis, censoring will be performed using the rules described in Table 2-4 or first dose for subjects without any adequate post baseline assessments.

PFS will be censored at the last adequate tumor assessment if one of the following occurs: absence of event; the event occurred after two or more missing tumor assessments. The term “missing adequate tumor assessment” is defined as a tumor assessment (TA) not performed or tumor assessment with overall lesion response of “UNK”. The rule to determine number of missing TAs is based on the time interval between the date of last adequate tumor assessment and the date of an event. If the interval is greater than twice the protocol-specified interval between the TAs and 2 times the protocol-allowed time window around assessments, then the number of missing assessments will be 2 or more.

If there is no adequate baseline assessment, the subject will be censored at their date of the first dose. Subjects without any adequate post baseline tumor assessments will be censored at the date of the first dose. Subjects who progressed or died after an extended period without adequate assessment will be censored at their date of last adequate assessment prior to progression or death even if subsequent information is available regarding progression or death. An adequate assessment is defined as an assessment where the investigator determined response is CR, PR, or SD. The date of response at that assessment will be used for censoring. As the assessment schedule changes through the course of the protocol (i.e. every 8 weeks until week 56 and then every 12 weeks thereafter), the following rules will be used for identifying extended loss to follow up or extended time without an adequate assessment (i.e. two or more missed assessments).

- If death or PD is on or prior to day 399 (week 56 + 7 day window), then a subject will be identified as an extended loss to follow up if the subject did not have an adequate

assessment during the time period of 119 days (16 weeks + 7 day window) prior to death or PD;

- Else if death or PD is after day 399 (week 56 + 7 day window) and prior to day 567 (week 80 + 7 day window), then a subject will be identified as an extended loss to follow up if the subject did not have an adequate assessment during the time period of 147 days (8 weeks + 12 weeks + 7 day window) prior to death or PD.
- Else if death or PD is after day 567 (week 80 + 7 day window), then a subject will be identified as an extended loss to follow up if the subject did not have an adequate assessment during the time period of 175 days (24 weeks + 7 day window) prior to death or PD.

For subjects who receive subsequent anti-cancer therapy the following rules will apply:

- If the start date of the anti-cancer therapy is partial (i.e. either missing the day but has the month and year available or missing both day and month), the imputation rules described in Section 5.1 will be applied. No imputation will be made for completely missing dates.
- If anti-cancer therapy is started without documented disease progression or is started prior to documented disease progression, then PFS will be censored at the date of the last adequate assessment that is no later than the date of initiation of anti-cancer therapy (i.e. if an assessment occurs on the same day as the start of new anti-cancer therapy the assessment will be used - as it will be assumed the assessment occurred prior to the administration of new anti-cancer therapy). The date of response at the last adequate assessment will be used as the censoring date.
- If a subject has only a baseline visit or does not have an adequate assessment that is no later than the date of initiation of anti-cancer therapy, PFS will be censored at the date of the first dose.

Refer to [Table 2-4](#) for censoring and event date options and outcomes for PFS.

Table 2-3 Outcome and event/censor dates for PFS analysis

Situation	Date	Outcome
No baseline assessment	Date of the first dose	Censored
Progression or death at or before next scheduled Assessment	Date of progression (or death)	Progressed
Progression or death after exactly one missing assessment	Date of progression (or death)	Progressed
Progression or death after two or more missing assessments	Date of last adequate assessment prior to missed assessment	Censored
No progression (or death)	Date of last adequate assessment	Censored
Treatment discontinuation due to 'Disease progression' without documented progression, i.e.	Date of last adequate assessment	Censored

Situation	Date	Outcome
clinical progression based on investigator claim		
New anticancer therapy given prior to protocol defined progression	Date of last adequate assessment on or prior to starting new anti-cancer therapy (or crossover treatment)	Censored
Death before first PD assessment (including death at baseline or prior to any adequate assessments)	Date of death	Progressed

Overall survival (OS)

If a subject is not known to have died at the time of analysis cut-off, then OS will be censored at the date of last known date subject was alive, i.e., last contact date (see [Table 2-1](#)).

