Refer to the Time and Events Table ([Table 20](#)) for the timing of all assessments. Assessments must be performed on a calendar schedule; delays in treatment administration will not delay performance of assessments. Details on efficacy and safety assessments are presented in [Section 7.2](#) and [Section 7.3](#), respectively. [REDACTED]

[REDACTED] Further details of study procedures and assessments can be found in the SPM.

[figure not shown]
Investigators may be requested to perform additional safety tests during the course of the study based on newly available data to ensure appropriate safety monitoring. Appropriate local regulatory and ethical approvals should be obtained before any additional testing is performed.

[Table 20](#) outlines study assessments and their timing.

Table 20 Time and Events Table

STUDY PHASES ¹	SCREENING ²	TREATMENT					FOLLOW-UP		
		Day 1	Day 15	Every 4 Weeks	Every 8 Weeks	Every 12 Weeks	Treatment Discontinuation ²⁷	Contact	Conclusion
Visit Window (Days)	(≤ 28 except where noted) ²		(± 3)	(± 3)	(± 7)	(± 7)	(± 7)	(± 7)	N/A
CLINICAL ASSESSMENTS¹									
Informed consent ³	X								
Demographic data	X								
Past and current medical conditions including cardiovascular medical history and risk factors	X	X ⁴							
Family history (cardiac, cancer)	X								
Disease characteristics ⁵	X								
Prior anti-cancer therapies	X								
Tumor tissue for BRAF V600 mutation testing (required for eligibility) ⁶	X								
Brain MRI/CT ⁷	X				X ⁷				
Lesion assessment ⁸	X	Week 8, and every 8 weeks through Week 56, then every 12 weeks thereafter (all ± 7 days) until disease progression							
Performance status (ECOG)	X	X ⁴		X			X		
Enrollment		X							
SAFETY ASSESSMENTS¹									
Physical examination ⁹	X (Complete)	X ⁴		X (Brief)			X (Complete)		
Dermatological examination (including skin lesion photography) ¹⁰	X				X		X		
Ophthalmic examination ¹¹	X			X Only at week 4					
Vital signs ¹²	X			X			X		
Adverse events ¹³	X	X		X			X	X	X
Concomitant medications ¹⁴	X	X		X			X	X	

STUDY PHASES ¹	SCREENING ²	TREATMENT					FOLLOW-UP		
		Day 1	Day 15	Every 4 Weeks	Every 8 Weeks	Every 12 Weeks	Treatment Discontinuation ²⁷	Contact	Conclusion
Visit Window (Days)	(≤ 28 except where noted) ²		(± 3)	(± 3)	(± 7)	(± 7)	(± 7)	(± 7)	N/A
ECG ¹⁵	X (5 weeks)		X	X (only at Week 4, 8 and 12)		X (after week 12)	X		
ECHO ¹⁶	X (5 weeks)			X (only at Week 4)		X			

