7.2.2 Efficacy Assessments

Disease progression and response evaluations will be determined according to the definitions established in RECIST, version 1.1 [Eisenhauer EA 2009].

Refer to the Time and Events Table (Table 20) for the schedule of efficacy assessments.

Assessments must be performed on a calendar schedule and should not be affected by dose interruptions/delays. For post baseline assessments, a window of ± 7 days is permitted to allow for flexible scheduling.

- The following scans/assessments are required at baseline: contrast CT (preferred method) of chest/abdomen/pelvis or MRI of abdomen/pelvis and any area of known disease, skin lesion photography, and clinical disease assessment for palpable lesions. Exception: If a chest CT cannot be performed, chest X-ray can be used only to document **the absence of disease** (no tumor lesions) or the **presence of new lesions**. If lesions are detected at baseline by chest X-ray, chest CT must be done to properly document these lesions at baseline and in follow-up tumor assessments. At each post-baseline assessment, evaluations of the sites of disease identified by these scans are required.

- A baseline brain scan is required for all subjects. For subjects without CNS disease at baseline, subsequent brain scans should only be performed as clinically indicated (e.g. symptoms suggestive of CNS progression). For subjects with CNS disease at baseline, a brain scan is required every 8 weeks or as clinically indicated. In addition, in order to confirm a CR in a subject with brain disease at baseline, a brain scan must be performed 1 week prior to the 1st set of images showing CR to 4 weeks after the next protocol specified assessment.
- If clinically indicated, a contrast enhanced CT or MRI scan of affected bone areas will be required at baseline. Bone lesions, if present as non-target lesions, will continue to be followed consistently throughout the study until disease progression, death, or withdrawal of consent.

Confirmation of CR and PR are required per protocol. Confirmation assessments must be performed no less than four weeks after the criteria for response have initially been met and may be performed at the next protocol scheduled assessment. If a confirmation assessment is performed prior to the next protocol schedule assessment, the next protocol scheduled evaluation is still required (e.g., evaluations must occur at each protocol scheduled time point regardless of unscheduled assessments).

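### SAP 2.7.3 sets two incompatible limits for two or more missed assessments (two visit windows versus one), so the bullets can censor an in-window progression after a single missed scan

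*SAP*

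**What the plan says.** Three parts of SAP 2.7.3 bear on the same question.

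- **General rule.** Two or more assessments count as missing on this condition: "If the interval is greater than twice the protocol-specified interval between the TAs and 2 times the protocol-allowed time window around assessments".
- **Bullets.** A few lines later the SAP gives day-specific rules for identifying extended loss to follow-up or "extended time without an adequate assessment (i.e. two or more missed assessments". For an event up to day 399 the look-back is an adequate "assessment during the time period of 119 days (16 weeks + 7 day window) prior to death or PD". For an event after day 399 and before day 567 it is an adequate "assessment during the time period of 147 days (8 weeks + 12 weeks + 7 day window) prior to death or PD". For an event after day 567 it is an adequate "assessment during the time period of 175 days (24 weeks + 7 day window) prior to" the event.
- **PFS outcome table** (captioned Table 2-3, cited as Table 2-4). The row "Progression or death after exactly one missing assessment" is an event on its own date. The next row censors only after two or more.

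The schedule is in Protocol Table 20: "Week 8, and every 8 weeks through Week 56, then every 12 weeks thereafter (all ± 7 days) until disease progression". Protocol 7.2.2 repeats the window: "For post baseline assessments, a window of ± 7 days is permitted to allow for flexible scheduling". Protocol 9.3.5.1.2 leaves the censoring detail to the SAP, so it does not settle which limit applies. DOR takes over the PFS rule (SAP 2.7.1 and 2.7.3).

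**The concern.** The general rule allows two visit windows and the bullets allow one, yet both claim to identify the same thing. A gap between the two limits is an event under one and a censoring under the other.

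Two windows are what a scan-detected progression needs: the last adequate scan may be up to 7 days early and the progression scan up to 7 days late, with both visits compliant. With one window, a documented progression after a single missed scan can be moved back to a censoring 120 days or more earlier. That removes a Kaplan-Meier step and generally raises the PFS or DOR curve from that date on.

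**Working it through.** **Inputs.** Intervals of 56 days through Week 56 and 84 days after (Protocol Table 20); window ±7 days (Protocol Table 20 and 7.2.2). Week w is taken as day 7w, as the SAP does (Week 56 + 7 = day 399).

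**1. The bullets' own figures reproduce.** 16×7 + 7 = 119; (8+12)×7 + 7 = 147; 24×7 + 7 = 175. Bands: 56×7 + 7 = 399; 80×7 + 7 = 567.

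**2. The general rule**, reading its 'and' as a sum:

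| Intervals spanned | General rule | Bullet | Gaps in conflict (days) |
|---|---|---|---|
| 8 + 8 weeks | 2×56 + 2×7 = 126 | 119 | 120–126 |
| 8 + 12 weeks | 56 + 84 + 14 = 154 | 147 | 148–154 |
| 12 + 12 weeks | 2×84 + 2×7 = 182 | 175 | 176–182 |

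The general rule names no mixed interval; 154 is its natural extension. Reading 'and' as two separate conditions gives limits of 112 and 168 days, which do not match the bullets either.

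**3. Example.** Last adequate scan at Week 8 minus 7 days: 56 − 7 = day 49. Week 16 missed. Progression at Week 24 plus 7 days: 168 + 7 = day 175. Gap 175 − 49 = 126 days.

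- General rule: 126 does not exceed 126, so event.
- Outcome table: one missing assessment, so event.
- First bullet: no adequate assessment in the preceding 119 days, so censored at day 49.

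**4. How often.** Let a and b be the deviations of the last adequate scan and the progression scan, each from −7 to +7: 15×15 = 225 combinations. A bullet that uses the right intervals censors when b − a is 8 to 14. The count is 7+6+5+4+3+2+1 = 28, and 28/225 = 12.4% if all combinations are equally likely. The documents give no visit-timing data, so that is an assumption. With two windows, matched to the intervals actually spanned, none of the 225 is censored in any visit pattern.

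**5. The bands add a separate problem at Week 80.** Last adequate scan at Week 56 (day 392), Week 68 missed, progression at Week 80 (day 560): the gap is 168 days with both scans exactly on time. Day 560 is before day 567, so the 147-day limit applies and the progression is censored. All 14×15 = 210 in-window combinations with progression on days 553–566 are censored. Day 567 itself falls in no band. Raising 147 to 154 would not cure this, since 168 exceeds 154. Counting weeks from day 1 instead of day 0 changes a few of these counts but not the conclusion.

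**6. Deaths go both ways.**

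- Scan on time at Week 8 (day 56), Weeks 16 and 24 missed. The Week 24 window closes on day 168 + 7 = 175. Death on days 176–182 is a gap of 120–126 days after two missed assessments. The table censors it, and so does the 119-day bullet; a 126-day limit would count an event.
- Scan at day 49, Week 16 missed, death on days 169–175: the gap is again 120–126 days, but the Week 24 window is still open and only one assessment is missed. The table gives an event; the bullet censors.

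**The case against.** The best defence is that the bullets are the operative algorithm. The SAP introduces them as the rules to be used because the schedule changes, whereas the earlier sentence is generic and names no interval. A programmer would most naturally code the bullets. That stands, and it weakens any suggestion that the output is a toss-up between two sentences. It does not rescue the text, because the bullets still contradict the outcome table in the example above.

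The Week 8 to Week 24 example is also the extreme corner. In the ordinary patterns the conflict needs the two dates to diverge by 8 to 14 days together. That is right, and it limits the size.

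A reader might infer that one or two subjects per endpoint would be reclassified. The documents do not support this, because they give no missed-scan rate. Expecting one reclassification takes about 225/28 ≈ 8 progressions that follow exactly one missed scan. If all 65 subjects progressed and 5% to 10% of progressions were of that kind (assumption), the expected number is 65×0.05×0.124 ≈ 0.4 to 65×0.10×0.124 ≈ 0.8, with fewer for DOR, which covers responders only.

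A reader might also infer that every death in the seven-day bands is wrongly censored. Step 6 shows otherwise: for some of these deaths the bullets agree with the table and the longer limit does not.

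Finally, the stakes are modest. PFS and DOR are secondary and descriptive, and this is the close-out SAP, written after the primary report.

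**Conclusion.** The inconsistency is real and rests on arithmetic alone: 126, 154 and 182 days against 119, 147 and 175 for one concept, with the shorter set contradicting the SAP's own outcome table for an in-window progression after one missed scan.

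The 12.4% is conditional on such a progression at the next scheduled scan, excludes the Week 80 pattern, and assumes uniform visit timing. The number of subjects affected cannot be derived and may be zero.

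The documents do not support extending the point to the primary endpoint or to OS, since neither uses this rule. Nor do they show that any reported PFS or DOR estimate is materially wrong. It is a definite fault in the definition of two secondary endpoints that should be corrected because doing so is cheap.

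**What to change.** Keep one rule in SAP 2.7.3, consistent with the outcome table, and delete the other.

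- **Preferred.** Count missed scheduled visits directly for both progression and death. A visit is missed if its window closed before the event without an adequate assessment; the visit at which progression is found is not counted. None or one missed is an event; two or more is censored at the last adequate assessment. A death after two closed and missed windows is then still censored.
- **Alternative, for progression found at a scan.** Set the look-back to the sum of the two scheduled intervals actually spanned after the last adequate scan, plus 14 days: 126, 154 or 182. This replaces both the one-window figures and the fixed day-399 and day-567 bands. Deaths need the visit-count rule.

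DOR follows through the existing cross-reference. If programming is already complete, state which rule was used and list any subject whose status differs under the other. The cost is SAP wording and reprogramming of the three bullets, with no new data.

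### SAP 2.7.3, read literally, censors at first dose early PFS failures that the outcome table counts as events; both the first-dose sentence and the 119-day look-back need an explicit condition

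*SAP*

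**What the plan says.** The sentence at issue is in SAP 2.7.3: "Subjects without any adequate post baseline tumor assessments will be censored at the date of the first dose". The same paragraph gives the definition: "An adequate assessment is defined as an assessment where the investigator determined response is CR, PR, or SD". Progression is therefore never an adequate assessment.

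Other text bearing on the same subjects:

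- The opening sentence of 2.7.3 gives the same first-dose rule with a condition attached: "For subjects who have not progressed or died at the time of the PFS or DOR analysis, censoring will be performed". SAP 2.7.1 censors PFS only where no event has been observed. Protocol 9.3.5.1.2 limits first-dose censoring to subjects who have not progressed or died. It also censors subjects with extended loss to follow-up before an event.
- The first extended-loss bullet in 2.7.3 flags a subject with no adequate "assessment during the time period of 119 days (16 weeks + 7 day window) prior to death or PD". The lead-in to the bullets describes what they are meant to find: "extended loss to follow up or extended time without an adequate assessment (i.e. two or more missed assessments".
- A general rule earlier in 2.7.3 counts two or more missing assessments "If the interval is greater than twice the protocol-specified interval between the TAs and 2 times the protocol-allowed time window".
- The PFS outcome table at the end of 2.7.3 treats these rows as events: "Progression or death at or before next scheduled" assessment, and "Progression or death after exactly one missing assessment". Its last row makes death before the first progression assessment an event and expressly includes deaths before any adequate assessment. Another row censors progression or death that follows two or more missing assessments.

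**The concern.** One subject can receive two outcomes. A first scan showing progression leaves the subject with no adequate post-baseline assessment, so the quoted sentence censors at first dose while the table records an event on the progression date. The same conflict arises for progression after one missed or unknown scan and for an early death before any adequate scan.

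These are the earliest failures in the trial. Censoring them at first dose takes them out of the risk set before they can count, so the PFS curve can only move up. The SAP does not say whether text or table prevails.

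**Working it through.** The plan states no PFS event count or power to reproduce, so the check has two parts: apply each rule to the affected cases, then size the effect.

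**Rules applied.** Scans fall at Week 8 and every 8 weeks to Week 56, each ±7 days (Protocol Table 20). Days are counted from first dose. No subject below has a CR, PR or SD after baseline.

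| Case | Quoted sentence, literal | 119-day look-back, literal | Outcome table |
|---|---|---|---|
| PD at Week 8 (day 56) | censored at first dose | flagged | event |
| Week 8 missed or unknown, PD at Week 16 (days 105–119) | censored at first dose | flagged | event |
| Death at day 29, before any scan | censored at first dose | flagged | event |
| Two scans missed, PD at Week 24 (days 161–175) | censored at first dose | flagged | censored |
| Two scans missed, death at day 149 | censored at first dose | flagged | two rows, opposite outcomes |
| Alive, no PD | censored at first dose | not applicable | censored |

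The look-back flags the first three cases because a subject with no CR, PR or SD at all has none in the preceding 119 days. Its own lead-in shows that this is not meant: at most one assessment has been missed.

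**Look-back length.** The bullet gives 16 × 7 + 7 = 119 days. The general rule gives 2 × 56 + 2 × 7 = 126 days. Counted from first dose for subjects with no adequate scan, both leave PD at days 56, 105 and 119 and death at day 29 as events, and both flag PD at days 161 and 175. They differ only for an event on days 120 to 126, where no scheduled scan falls: PD at day 123 is censored under 119 and an event under 126.

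**Size if the literal text is programmed.** Take N = 65 (SAP 1.1) and k affected subjects. If nobody else is censored before the last of these k failures, the Kaplan-Meier estimate after it is (number still event-free)/65 with them as events and (number still event-free)/(65 − k) without them. The ratio is 65/(65 − k). A simulated 65-subject curve at 12 months gave 1.0156, 1.0317 and 1.0656 for k = 1, 2 and 4, matching the formula.

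Medians depend on the shape of the curve. Two models were used, with the combination-arm medians in Protocol 1.2.3 (9.3 and 11.4 months) as the correct values:

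- Exponential from first dose: literal median = m × [1 − log2(1 − k/65)].
- Failures by Week 8, the rest exponential from t0 = 56/30.4375 = 1.84 months: rate = ln[2(1 − k/65)]/(m − t0), literal median = t0 + ln 2/rate.

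| k | 65/(65 − k) | m = 9.3: first / second model | m = 11.4: first / second model |
|---|---|---|---|
| 0 | 1 | 9.30 / 9.30 | 11.40 / 11.40 |
| 1 | 1.016 | 9.51 / 9.47 | 11.65 / 11.62 |
| 2 | 1.032 | 9.72 / 9.65 | 11.91 / 11.85 |
| 4 | 1.066 | 10.15 / 10.05 | 12.44 / 12.36 |

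A 12-month rate of 41% (Protocol 1.2.3) would read 41 × 65/64 = 41.6% at k = 1 and 41 × 65/61 = 43.7% at k = 4.

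**Plausible k.** Protocol 1.2.3 reports 0% progression at first assessment on the combination in Part C of BRF113220 (162 subjects, three arms). Assuming equal arms, 162/3 = 54, the two-sided 95% upper limit for 0/54 is 1 − 0.025^(1/54) = 6.60%, or 0.066 × 65 = 4.3 subjects. This covers first-scan progression only. It also assumes that the rate carries over to East Asian subjects, including those with acral melanoma, so it does not bound k.

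**The case against.** The best defence is that the SAP already supplies the missing condition. The opening sentence of 2.7.3, SAP 2.7.1 and Protocol 9.3.5.1.2 all carry it, and 2.7.3 sends the reader to the table for outcomes. A programmer would have to set aside three conditional statements and three table rows to go wrong, and nothing suggests that anyone did. PFS is descriptive, and the only documented rate of first-assessment progression on the combination is zero.

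Most of this stands: the intent for the three early-failure cases is clear, and the effect is hypothetical. It does not make the sentence safe, because its neighbours do censor despite events. The sentence before it censors subjects without an adequate baseline regardless of outcome, and the table agrees. The sentence after it censors even where later progression or death is known. Restricted to event-free subjects, the quoted sentence would only repeat the opening one, so a reader could reasonably take it to mean more.

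Two stronger readings are tempting. A reader might infer that this sentence alone is at fault; the look-back, taken equally literally, catches the same subjects. A reader might also infer that the table's last row makes every death without an adequate scan an event, because the censoring row calls for a last adequate assessment date that such a subject lacks. That is an inference. The row for two or more missing assessments names deaths too, Protocol 9.3.5.1.2 censors after extended loss to follow-up, and no order of precedence is given. The documents leave late deaths open.

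**Conclusion.** The point holds as a drafting error that should be fixed. For first-scan progression, progression after exactly one missed or unknown scan, and early death before any adequate scan, the literal text contradicts the table, and the weight of the documents favours counting an event. For deaths with no adequate scan after two or more missed assessments, the table contradicts itself.

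Any bias would be upward and confined to PFS. ORR keeps these subjects in the denominator as non-responders, OS has its own censoring rule, and every subject in the DOR analysis has a CR or PR scan. At k = 4 the median would rise by about 0.75 to 1.0 month across the two models and two reference medians; at k = 0 nothing changes. These figures are illustrations that rest on N = 65, an assumed k, and the literal text having been programmed. A reader might infer that reported PFS is inflated. The documents do not support that: they show neither k nor how these subjects were derived in the primary analysis.

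**What to change.** 1. Limit the quoted sentence to subjects with no adequate post-baseline assessment and no documented progression or death.
2. State that the outcome table governs. Progression at the first post-baseline scan, progression after exactly one missed scan, and death before two assessments have been missed are then events on their own dates.
3. Where there is no adequate post-baseline scan, count the extended-loss interval from first dose, and choose one length, 119 or 126 days.
4. Reconcile the two table rows that give opposite outcomes for a death with no adequate scan after two or more missed assessments, and state which applies. This is for the SAP authors to decide.
5. Check that the programmed derivation follows the reconciled rule.

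The cost is a short wording edit and a program check, with no new data. For the early failures, reported PFS changes only if the literal text was programmed. Items 3 and 4 could also change how an event on days 120 to 126 or a late death with no adequate scan is classified, if any occurred.

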Duration of response (DOR) only applies to subjects whose confirmed overall response is complete response (CR) or partial response (PR) according to RECIST 1.1 based on local investigators review of tumor assessment data. The start date is the date of first documented response of CR or PR (i.e., the start date of response, not the date when response was confirmed), and the end date is defined as the date of the first documented progression or death. Subjects continuing without progression or death due to underlying cancer will be censored at the date of their last adequate tumor assessment using the censoring rule described for PFS analysis (See Section 2.7.3 for additional details).

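### SAP 2.7.3 censors progression at Week 80 after one missed scan, against its own outcome table, and leaves day 567 outside all three bullets

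*SAP*

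**What the plan says.** Protocol Table 20 schedules lesion assessments every 8 weeks to Week 56 and every 12 weeks after that, each within ±7 days. The visits around the change are Weeks 48, 56, 68, 80 and 92.

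SAP 2.7.3 deals with progression (PD) or death after missed scans in three places:

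- **General rule.** It infers the number of missed scans from the gap between the last adequate scan and the event: "If the interval is greater than twice the protocol-specified interval between the TAs and 2 times the protocol-allowed time window around assessments", at least two scans count as missed.
- **Three bullets**, introduced because the schedule changes, for "identifying extended loss to follow up or extended time without an adequate assessment (i.e. two or more missed assessments". For events up to day 399 the look-back is 119 days. For events "after day 399 (week 56 + 7 day window) and prior to day 567 (week 80 + 7 day window" a subject is flagged who "did not have an adequate assessment during the time period of 147 days (8 weeks + 12 weeks + 7 day window" before the event. For events after day 567 the look-back is 175 days.
- **Outcome table.** "Progression or death after exactly one missing assessment" is an event on its own date. Progression or death after two or more missed scans is censored at the last adequate scan.

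SAP 2.7.1 carries this over to DOR, "using the censoring rule described for PFS analysis".

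**The concern.** The second bullet's 8+12-week look-back suits Week 68, whose two preceding intervals are 8 and 12 weeks. Its range of days runs on through almost all of the Week 80 window, where the two preceding intervals are 12 and 12 weeks. One missed scan before Week 80 then looks like two, and a documented progression is censored at Week 56. That contradicts the purpose given for the bullets, the outcome table and the general rule, all within one section.

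Two smaller faults sit beside it. The second bullet stops before day 567 and the third starts after it, so that day has no bullet. And the bullets add one 7-day window where the general rule adds two.

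At stake are the later part of the PFS curve and the DOR curve, including the quartiles and time-point estimates that SAP 2.7.2 and 5.4.2 plan to report.

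**Working it through.** **Inputs.** Schedule and ±7 days from protocol Table 20. Day limits and look-backs from SAP 2.7.3. Week W is day 7W, as the SAP's own day 399 for Week 56 + 7 implies. A subject is flagged when the gap exceeds the look-back. Months are days / 30.4375 (SAP 2.1.3.4).

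**1. The SAP's figures reproduce.** 56×7+7 = 399; 80×7+7 = 567; 16×7+7 = 119; (8+12)×7+7 = 147; 24×7+7 = 175. The sums are right. The fault is the range of days to which 147 is applied.

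**2. PD on schedule after exactly one missed scan.**

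| PD at | Last scan | Gap (days) | Look-back | Bullets give | Outcome table gives |
|---|---|---|---|---|---|
| Week 56 | Week 40 | 392−280 = 112 | 119 | event | event |
| Week 68 | Week 48 | 476−336 = 140 | 147 | event | event |
| Week 80 | Week 56 | 560−392 = 168 | 147 | **censored** | event |
| Week 92 | Week 68 | 644−476 = 168 | 175 | event | event |

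**3. Visit windows do not rescue Week 80.** The shortest in-window gap is 553−399 = 154, still above 147. All 14×15 = 210 date pairs with PD on days 553 to 566 are censored. The 15 pairs with PD on day 567 meet no bullet. With Week W placed at day 7W+1 instead, 202 of 225 are censored, 15 meet no bullet and 8 are events; the on-schedule result is the same.

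**4. General rule at Week 80.** Both intervals are 12 weeks, so the limit is 2×84 + 2×7 = 182 days. The 168-day gap is an event.

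**5. Deaths.** 392+147 = 539, so deaths on days 540 to 566 (27 days) after an on-schedule Week 56 scan are censored, although the Week 80 window is still open and only Week 68 has been missed.

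**6. Where the curve changes.** The subject in step 2 moves from an event at 560/30.4375 = 18.4 months to censored at 392/30.4375 = 12.9 months. The earliest in-window Week 56 scan is day 385, or 12.6 months, so PFS before then is untouched by this fault. The protocol (section 1.2.3) cites PFS medians of 9.3 and 11.4 months for the combination. DOR starts at first response, so it can change earlier: assuming a first response at Week 8 (day 56), DOR would be censored at (392−56)/30.4375 = 11.0 months instead of ending in an event at (560−56)/30.4375 = 16.6.

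**7. Week 80 lies within the final data.** A subject who met the 16-week condition at the 23-Feb-2018 cut-off (SAP 1.1) was first dosed by 3-Nov-2017. That subject is at study day 605 on 30-Jun-2019, the Mainland Chinese cut-off (SAP 2.1.1). Other subjects have no cut-off.

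**8. Rules compared.** PD after one missed scan has 14 visit combinations up to Week 164, with 15×15 = 225 date pairs each, or 3,150. PD after two missed scans has 13 combinations, or 2,925 pairs. Death-days take the last scan as on schedule, Weeks 8 to 80, and count a scan as missed once its window has closed.

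| Rule | One-missed PD pairs censored | Two-missed PD pairs left as events | Death-days censored after one missed | Death-days left as events after two missed |
|---|---|---|---|---|
| Current | 574 (15 more under no bullet) | 0 (15 under no bullet) | 27 | 28 |
| Bullet 2 ends day 532; 119/147/175 | 392 | 0 | 0 | 28 |
| Bullet 2 ends day 532; 126/154/182 | 0 | 0 | 0 | 91 |

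Here 574 = 210 + 13×28 and 392 = 14×28. The 28 per combination come from the single window: they are the pairs whose gap lies in the top 7 days of the allowed range. The 28 death-days are days 400 to 427 after a Week 40 scan. The 91 are 35 after Week 40 plus 7 after each of eight other visits. Date pairs list possible dates; they are not frequencies.

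**The case against.** **Day 567 is not unregulated.** A reader might infer that the SAP has no rule for that day. It has no bullet, but the general rule and the outcome table still apply. This objection stands; what remains is a gap in the bullets.

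**The general rule already settles Week 80.** It does, at 182 days, because no 8-week interval lies between Weeks 56 and 80. That does not rescue the bullet. The bullets are the specific instruction for the changed schedule, so a programmer would code them, and they then override the general rule exactly where the two disagree.

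**It may be a deliberately cautious choice.** The SAP gives no such reason, and the same 168-day gap is an event at Week 92. Dropping a documented progression also raises the curve after that date.

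**The count of 574 overstates the fault.** This stands. Of the 574, 364 (63%) come from the one-window versus two-window mismatch, and none of the counts measures how often such dates occur.

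**The effect is narrow.** This also stands. It needs an adequate Week 56 scan, Week 68 missed, no adequate unscheduled scan in the look-back, and PD at Week 80 or an event a little before it. With about 65 subjects the number affected could be zero.

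**Conclusion.** Wrong as written. For PD at Week 80 after only Week 68 is missed, the second bullet gives the opposite result to the outcome table and the general rule. An affected subject changes from an event at 18.4 months to censored at 12.9 months. Deaths on 27 days (540 to 566) after an on-schedule Week 56 scan are censored in the same way. Day 567 is covered only by the general rule. The window mismatch is a separate, smaller inconsistency.

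The consequence is limited to PFS and DOR, for which "PFS, OS and DOR will be summarized descriptively using Kaplan-Meier medians and quartiles" with no formal testing. A reader might infer that the trial's main result or its median PFS is biased. The documents do not support that: ORR does not use this rule, and a PFS median near the cited values lies before 12.6 months. The upper PFS quartile, late time-point estimates and DOR could move. By how much cannot be derived, because the documents do not say how many subjects missed Week 68 and then progressed or died near Week 80. The statement about the median assumes that this population's PFS is close to the cited trials'. The day counts assume that Week W is day 7W.

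**What to change.** End the second bullet at day 532 and apply the third bullet to all days after 532, keeping 119/147/175. Day 532 is the earliest in-window Week 56 scan plus the look-back (385+147), so up to that day the 147-day rule never flags a subject whose Week 56 scan was in window. On-schedule PD at Week 80 after one missed scan becomes an event, PD after two missed scans stays censored, day 567 is covered, and misclassified death-days fall from 55 (27+28) to 28.

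Then make the window count agree, and state which option is chosen:

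- **One window.** Reword the general rule to one window. This still censors 28 of 225 date pairs at each one-missed PD visit.
- **Two windows.** Use 126/154/182 with the same day-532 limit. This censors no one-missed PD pair, but leaves 91 death-days after a second missed scan as events, against 55 misclassified now.

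The outcome table stays as it is. The cost is one day limit plus either one reworded sentence or three constants, and the matching program constants; no new data are needed. SAP section 1 says that decisions precede database lock, so the change belongs before lock. If lock has passed, record it in SAP section 4 and show PFS and DOR under both rules.
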